9.0 Efficacy Analyses

9.1 General Considerations

The primary efficacy analyses will be conducted in the EAS-SF and EAS-SF-SUPP for the supplementary analysis of the stool fat. All other efficacy analyses will be conducted

in the FAS population, considering different groups for different analysis as tabulated in Table 2 in Section 4.2. All tests will be 2-sided at an alpha level of 0.05.

The Primary Analysis and other analyses will be performed after all subjects in the resected and non-resected population have completed the study and the database has been locked. This will be the only and final analysis for the primary and secondary efficacy endpoints as well as all other efficacy endpoints in the study.

"Baseline" refers to the last non-missing observation before the first administration of study drug or randomization if no study drug is given, unless otherwise specified in the individual analysis section.

9.2 Handling of Missing Data

Missing data will be imputed using the following methods for the efficacy analyses.

9.2.1 Adjustment for Missing Stool Fat Samples in Stool Fat per Day

The stool fat (g) will be reported for each subject per 24 hours period for 2 consecutive 24-hour collection periods (total 48-hour period) separately, prior to both Baseline (Day 1) visit and Week 1 (Day 8) visit. The average daily stool fat (g/day) at both Baseline and Week 1 visit will be calculated from these two reported 24-hour stool fat for each subject.

Step 1: The two reported 24-hour stool fat value will be assessed to see whether they are evaluable values at both Baseline and Week 1 based on the stool frequency and number of stool sample missed to be collected for the corresponding 24-hour period, following the rules in Section 9.3.2.1.

Step 2: If the reported 24-hour stool fat value is deemed to be evaluable but there are missing stools in that 24-hour collection period, the adjusted 24-hour stool fat will be calculated as following:

$$x = \frac{y}{p} * 100$$

where,

x: Calculated adjusted stool fat for a 24 hour period

p: Percentage of stool sample collected in a 24 hour period

y: Laboratory reported 24-hour stool fat from the stool samples collected in a 24 hour period

If a subject has evaluable 24-hour stool fat value for both days for a visit, then the stool fat for that visit will be determined based on the average of the two evaluable value (with adjustment if needed as described in Step 2 above). If subject has only one evaluable 24-hour stool fat value for a visit, then the stool fat for that visit will be determined based on that evaluable value (with adjustment if needed as described in Step 2 above). If both 24-hour stool fat values for that visit are not evaluable, then subject is considered having no evaluable stool fat data for that visit with no imputation.

9.2.2 Missing EPI Symptoms Score

The EPI Symptoms Questionnaire data will be used to compute the EPI Symptom score. Each of the 12 questions is scored as described in Dose modification, Section 2.5. The missing answers to any of the 12 questions of the EPI questionnaire will not be possible unless the subject did not complete the EPI questionnaire at all. The questionnaire can be submitted only when all the questions in the questionnaire have been answered. No questions can be skipped before submitting. Missing EPI questionnaire will not be imputed.

9.2.3 Missing Stool Frequency

Daily stool frequency will be collected from Day -7 through Day -1, Day 1 through Day 7 and for 7 days prior to each subsequent visit. For the stool frequency analysis, the mean frequency for 3 days prior to each visit (for example, Day -3, -2, -1 will be

considered for Baseline, and Day 5, 6, 7 for Week 1) is considered. If stool frequency data for any of the 3 days prior to each visit is not available, then the missing value is estimated using the following criteria.

- If data for none or only 1 day is available for a visit, then the mean stool frequency for the visit will be considered as missing.
- If data for 2 days of the 3 required days are available, then the mean stool frequency for the visit will be calculated based on the data from the 2 available days.

For the supplementary analysis of the stool frequency, the mean stool frequency for each week is considered. If stool frequency data for all 7 days in a week is not available, then the missing value is estimated using the following criteria.

- If data for 50% or less i.e., three or less days are available for each week, then the mean stool frequency for the week will be considered missing for the analysis.
- If data for more than 50% i.e., 4 or more days are available, then the stool frequency for the missing days will be imputed using the mean value of the available data. Finally, the mean stool frequency for the week will be calculated.

9.2.4 Missing Stool Consistency

Daily stool consistency will be collected once daily from Day -7 through Day -1, Day 1 through Day 7 and for 7 days prior to each subsequent visit. For the stool consistency analysis, the proportion of watery stool consistency among the 7 days prior to each visit (for example, Day -7 to -1 will be considered for Baseline, and Day 1 to Day 7 for Week 1) is considered. For example, among the 7 days for a visit if 6 of those days have watery consistency, then the proportion of days with watery stool consistency will be 6/7. If stool consistency data for any of the seven days prior to each visit is not available, then the proportion of days with watery stool consistency will be estimated using the following criteria.

- If data for 50% or less i.e., 3 or less days are available for each week, then the mean stool consistency for the week will be considered missing for the analysis.
- If data for more than 50% i.e., 4 or more days are available, then the proportion of days with watery stool consistency will be determined based on the available data. For example, if 5 days data is available for a visit and 3 of those days have watery consistency, then the proportion of days with watery stool consistency will be 3/5.

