## 3.5 Patient-Reported Outcomes

---

Subjects will complete the self-administered patient-reported outcome (PRO) instruments (when allowed per local regulatory guidelines). Subjects should be instructed to follow the instructions provided with the instrument and to provide the best possible response to each item. Site personnel shall not provide interpretation or assistance to subjects other than encouragement to complete the tasks. Subjects who are functionally unable to read any of the instruments may have site personnel read the questionnaire to them. Site personnel will encourage completion of the instrument at all specified visits and will ensure that a response is entered for all items.

The PRO instruments to evaluate quality of life are the European Organisation for Research and Treatment of Cancer (EORTC) quality of life questionnaire (QLQ)-C30 ([Appendix B](#)) and EORTC QLQ-PAN26 ([Appendix C](#)).

The PRO instrument should be completed before drug administration on Day 1, Weeks 1, 5, and 9, as well as Week 13/premature discontinuation (PD) and before any discussion of adverse events or any review of laboratory findings.

EPI symptoms (using EPI Symptom Questionnaire) will be assessed at visits indicated in Section [2.1](#). The subject should complete the questionnaire before site personnel perform any clinical assessments and before any interaction with site personnel occurs to avoid biasing the subject's response. Site personnel will administer the EPI Symptom Questionnaire ([Appendix D](#)) to subjects.

Food intake, stool frequency, stool consistency and incidences of diarrhea will be collected by subjects daily for a week prior to the following visits; Day 1, Weeks 1, 5, 9, and 13. For stool consistency, subjects will select the image from the Bristol Stool Chart that represents the most frequent or average stool consistency during a past 24-hour period.

Study drug intake will be recorded daily, by subjects using the ePRO device, during the treatment period, starting on Day 1 through Week 13.

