3.2 Secondary Endpoint(s)

Resected Pancreatic Cancer Subjects

- Change from Baseline to Week 1 in average daily stool frequency. The average daily stool frequency is calculated from the last 3 days prior to each of Baseline and Week 1 visit.
- Change from Baseline to Week 1 in stool consistency, based on the proportion of days having watery stool consistency in the last 7 days prior to each of Baseline and Week 1 visit.
- Change from Baseline to Week 1 in the total EPI Symptoms Score.

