9.4.3 Stool Consistency

Stool consistency will be collected once a day for 7 days prior to each visit using the Bristol Stool Chart and will be characterized based on the typology below for the analysis. The proportion of days with watery consistency during 7-day period prior to each visit will be calculated at each visit for each subject. The analyses will be performed using the population and treatment groups as described in Table 1 in Section 4.2.

- A Wilcoxon paired signed rank test will be performed for comparison of the proportion of days with watery stool consistency of Week 1 to that at Baseline within each dose cohort in the resected population. Similar test will be performed in the non-resected population as well.
- For comparison of change in the proportion of days with watery stool consistency from Baseline to Week 1 between two dose cohorts will be assessed through the non-parametric Wilcoxon Rank-Sum test in the resected population.

- Descriptive statistics will be provided for proportion of days with watery stool consistency at Week 1 (Day 8), 5, 9 and 13 as well as change from Baseline for each visit in both the resected and non-resected population.
- The number and percentages of subjects with 7 different types of stool consistency reported and 2 different types of characterization of stool consistency as described in Table 3 will be summarized per day for 7 days prior to Baseline (Day 1) and 7 days prior to Week 1 (Day 8) visit for the non-resected population and for each analysis treatment group in the resected population.

Table 3. Characterization of Bristol Stool Chart for Analysis

Stool Type (Score)	Characterization
Type 1 (1), Type 2 (2), Type 3 (3), Type 4 (4), Type 5 (5)	Hard/Normal
Type 6 (6), Type 7 (7)	Watery

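### SAP 9.2.4 makes no provision for days without a bowel movement; applied as written, they leave the denominator of the watery-stool endpoint or cause the visit to be set to missing

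*SAP*

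**What the plan says.** The secondary endpoint for resected subjects is the change from Baseline to Week 1 in "the proportion of days having watery stool consistency in the last 7 days prior to each of Baseline and Week 1 visit" (SAP 3.2). SAP 9.4.3 repeats the 7-day basis: "The proportion of days with watery consistency during 7-day period prior to each visit will be calculated at each visit for each subject".

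The daily entry is a single picture. Operations Manual 3.5 (protocol Appendix F) says that "subjects will select the image from the Bristol Stool Chart that represents the most frequent or average stool consistency during a past 24-hour period". The chart in Operations Manual Appendix E has types 1 to 7. SAP Table 3 classes types 1 to 5 as hard or normal and types 6 and 7 as watery. None of these places provides for a day without a bowel movement.

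The missing-data rule in SAP 9.2.4 starts from "If stool consistency data for any of the seven days prior to each visit is not available". It has two branches. The first, "If data for 50% or less i.e., 3 or less days are available for each week", sets the week to missing. The second, for 4 or more days, says that "the proportion of days with watery stool consistency will be determined based on the available data", so it divides by the days with data; its example is "if 5 days data is available for a visit and 3 of those days have watery consistency", giving 3/5.

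SAP 9.2.3 collects daily stool frequency on the same days but does not link it to the consistency rule.

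**The concern.** The endpoint is defined over days, and a stool-free day is one of the 7 days and is not watery. It has no Bristol type, so under the wording of 9.2.4 it looks the same as a missed diary entry. It then shrinks the denominator, which raises the watery proportion, or it counts towards setting the visit to missing.

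Stool-free days may well depend on treatment. Stool frequency is itself a secondary endpoint, and protocol 2.2 reports lower average frequency on pancrelipase than on placebo. If such days increase after Baseline, or differ between doses, the rule affects both the within-cohort signed-rank test and the between-dose rank-sum test in SAP 9.4.3. The same derivation feeds the later-visit and non-resected summaries.

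**Working it through.** **Inputs from the documents.** 7-day window; watery means types 6 and 7; divide by days with data if 4 or more; missing if 3 or fewer. The documents give neither stool rates nor the share of stool-free days, so every rate below is an assumption.

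**1. The plan's own examples.** 6/7 = 0.857 and 3/5 = 0.600, as the rule states. If the two absent days in the second example were stool-free, the proportion over 7 days is 3/7 = 0.429. From a Baseline of 6/7, the change is 0.600 − 0.857 = −0.257 by the rule and 0.429 − 0.857 = −0.429 over 7 days.

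**2. Chance that a complete diary week is set to missing.** Let p be the daily chance of no stool, with days independent. Then P(missing) = P(Binomial(7, 1 − p) ≤ 3).

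| p | P(missing) |
|---|---|
| 5% | 0.02% |
| 10% | 0.3% |
| 20% | 3.3% |
| 30% | 12.6% |

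**3. Effect on the change from Baseline.** Let w be the share of stool-days that are watery. The 7-day proportion has mean w(1 − p); the rule returns about w. Assume Baseline w = 0.70 and p = 3%, so 0.70 × 0.97 = 0.679. Assume Week 1 w = 0.50 on low dose and 0.30 on high dose.

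- High dose with p = 20% at Week 1: 0.30 × 0.80 − 0.679 = −0.439 over 7 days; 0.30 − 0.70 = −0.400 by the rule.
- Between doses, by the rule: 0.30 − 0.50 = −0.200 in every case. Baseline cancels.
- Over 7 days, p = 3% in both: 0.291 − 0.485 = −0.194.
- 3% low vs 10% high: 0.270 − 0.485 = −0.215.
- 5% vs 20%: 0.240 − 0.475 = −0.235.
- 5% vs 30%: 0.210 − 0.475 = −0.265.
- Dose changes frequency only (w = 0.50 in both), 5% vs 20%: 0.400 − 0.475 = −0.075 over 7 days; 0.00 by the rule.

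**4. Size in terms of stools per day.** Assume Poisson daily counts with mean m, varying between subjects as a gamma with shape 4. The share of stool-free days is z(m) = (1 + m/4)^(−4): 0.081 at 3.5, 0.107 at 3.0, 0.143 at 2.5, 0.198 at 2.0 and 0.350 at 1.2. Assume w = 0.50 on low dose and 0.40 on high dose. The 7-day proportion is w(1 − z). The rule gives about 0.50 − 0.40 = 0.100 throughout. Shrinkage is 1 − 0.100/(7-day difference). The shares set to missing come from simulation. These are Week 1 values only.

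| Low vs high dose, stools/day | 7-day proportions | Difference | Shrinkage | Set to missing, low vs high |
|---|---|---|---|---|
| 3.5 vs 3.0 | 0.460 vs 0.357 | 0.102 | 2% | 2% vs 4% |
| 2.5 vs 2.0 | 0.428 vs 0.321 | 0.107 | 7% | 6% vs 10% |
| 3.0 vs 2.0 | 0.447 vs 0.321 | 0.126 | 20% | 4% vs 10% |
| 2.5 vs 1.2 | 0.428 vs 0.260 | 0.168 | about 40% | 6% vs 27% |

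**The case against.** **The SAP never says that it drops stool-free days.** Correct. The result follows from applying 9.2.4 literally to an entry with no value for such a day. Diary or programming specifications outside these documents might code it. That limits the claim to the rule as written, but the denominator of a secondary endpoint should be settled in the SAP.

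**The bias depends on the target.** Also correct. For the watery share among days with stool, the rule is essentially unbiased: it returns the assumed 0.50 and 0.40. But SAP 3.2 and 9.4.3 name days in a 7-day period, and nowhere a proportion among stool-days. Lower frequency is tested separately, which is a reason to report both quantities, not to leave the choice open.

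**Best responders.** A reader might infer that the rule deletes the best responders. The documents do not support this. Four or more stool-free days in a week may be constipation, which is item 6 of the EPI Symptom Questionnaire. What stands is that exclusion would depend on outcome.

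**A large loss of effect.** A reader might also take the 40% shrinkage as typical. It needs 35% stool-free days on one dose against 14% on the other. With smaller contrasts the shrinkage is 2% to 7%. If stool-free days are equally common in both cohorts, the between-dose difference is not understated (step 3: −0.200 by the rule, −0.194 over 7 days). Fewer stools per day need not mean more days with none.

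**Limited scope.** The primary endpoint is untouched, SAP 12.0 calls the study non-registrational, and SAP 9.4.2 already summarises daily frequency with its minimum. These points lower the priority but leave the derivation undefined.

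**Conclusion.** The point holds as a gap between the stated endpoint and the stated missing-data rule. As written, SAP 9.2.4 removes stool-free days from a proportion defined over 7 days and can set the visit to missing because of them. The change and the between-dose difference are understated only if stool-free days are more frequent after treatment or on the better dose. That is plausible, but the documents do not quantify it.

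In the scenarios examined, the between-dose loss runs from about 2% to about 40%, with 4% to 27% of the lower-frequency cohort set to missing. It reaches the whole effect if dose changes frequency alone. These figures rest on the assumed stool rates, Poisson counts, gamma spread and watery shares. The point should be settled, but it is confined to one secondary endpoint and its related summaries.

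**What to change.** Before unblinding, add to SAP 9.2.4 and 9.4.3:

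*A day with recorded stool frequency 0 counts as an available day without watery stool. A day with no frequency entry and no consistency entry, or with frequency of 1 or more and no consistency rating, is missing.*

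The second sentence is needed in full. A rule that calls only days with neither entry missing would count a day with recorded stools and no rating as not watery.

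Apply the 4-of-7 requirement to days available under this definition. Report stool-free days by visit and dose, and give the proportion among stool-days as a sensitivity analysis. Confirm that the diary, electronic or paper, distinguishes an entered zero from a blank.

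The cost is two sentences, a merge of two diary fields already collected and one extra summary. No new data are needed.

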9.2.5 Missing QoL Score (EORTC QLQ-C30 and QLQ-PAN26)

Refer to the score manual for the EORTC QLQ-C30 for imputing missing items (Appendix B).

9.3 Primary Efficacy Endpoint(s) and Analyses

9.3.1 Primary Efficacy Endpoint(s)

Resected Pancreatic Cancer Subjects

The primary endpoint is change in stool fat from Baseline (Day 1) to Week 1 (Day 8) for each dose cohort. Stool fat is collected during the 48 hours prior to the Day 1 (Day -2 and Day -1) and Week 1 (Day 6 and Day 7) visits.

9.3.2 Main Analysis of Primary Efficacy Endpoint (s)

The stool fat (g) for each subject for the 48 period prior both Baseline (Day 1) visit and Week 1 (Day 8) visit will be calculated according to Section 9.2.1. The change in stool fat from Baseline to Week 1 will be analyzed using an analysis of covariance (ANCOVA) model including treatment as a fixed effect and Baseline stool fat as the covariate. The least square mean estimates for change in stool fat along with its two-sided 95% CI will be provided for each treatment group. The hypothesis testing for a difference from baseline to Week 1 in stool fat will be tested at 2-sided 5% α -level for each treatment group in EAS-SF separately.

The attributes of the estimands corresponding to the primary efficacy endpoint are summarized in Table 2.

	Attributes of the Estimand				
Estimand	Population	Endpoint	Treatment	Intercurrent Events	Statistical Summary
Primary	Evaluable Analysis Set for Stool Fat (EAS-SF) in the Resected Pancreatic Cancer cohort.	Change in Stool Fat from Baseline (Day 1) to Week 1 (Day 8).	CREON (High Dose : 72,000 USP units (Lipase) with meals/36,000 USP units (Lipase) with snacks, Low Dose : 12,000 USP units (Lipase) with meals/ 6,000 USP units (Lipase) with snacks).	IE: Subjects with missing or incomplete (not evaluable) stool fat sample at either Baseline or Week 1 will be excluded from the analysis.	Mean Change in stool fat from Baseline to Week 1 for each dose cohort separately.

Table 2.Summary of the Estimand Attributes of the Primary Efficacy
Endpoint

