#### **Resected Pancreatic Cancer Subjects**

The primary endpoint is change in stool fat from Baseline (Day 1) to Week 1 (Day 8) for each dose cohort in Resected Subjects. Stool fat is collected during the 48 hours prior to the Day 1 and Week 1 visits.

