### Primary Analysis

The primary efficacy endpoint is the change in stool fat from Baseline (Day 1) to Week 1. Within each dose cohort, a paired t-test will be performed to test the null hypothesis that the mean stool fat change is equal to zero. For comparison between dose cohorts, the change from Baseline will be analyzed using an analysis of covariance model including treatment as a fixed effect and Baseline stool fat as the covariate.

Details on the primary and other efficacy analyses are provided in the SAP.

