1.0 Introduction

This Statistical Analysis Plan (SAP) describes the statistical analyses for CREON or ABT-SLV245 Study M16-142 titled "Creon® (pancrelipase) therapy for subjects with exocrine pancreatic insufficiency (EPI) due to pancreatic cancer: A double-blind, randomized, parallel design with 2 dose cohorts of pancrelipase in resected pancreatic cancer subjects and an open-label single dose cohort in non-resected pancreatic cancer subjects".

Study M16-142 examines the effects of Creon in subjects with resected pancreatic cancer receiving 2 dosing cohorts, and one dosing cohort in non-resected pancreatic cancer subjects.

The SAP will not be updated in case of administrative changes or amendments to the protocol unless the changes impact the analysis.

Unless noted otherwise, all analyses will be performed using SAS Version 9.4 (SAS Institute Inc., Cary, NC 27513) or later under the UNIX operating system.

This SAP includes changes to analyses described in the protocol version 3.0 dated 22 November 2019. Details are outlined in Section 12.0.

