2.0 Study Design and Objectives

2.1 Objectives, Hypotheses, and Estimands

The objective of this study is to evaluate the effects of Creon[®] (pancrelipase) on stool fat and EPI symptoms in subjects with resected pancreatic cancer receiving 2 dosing cohorts, and one dosing cohort in non-resected pancreatic cancer subjects.

The hypothesis for the primary objective of a significant change in stool fat from Baseline to Week 1 will be tested at 2-sided 5% α -level for each dose cohort in the resected pancreatic cancer population and for the non-resected population as well.

For each subject, the average stool fat per day (grams/day) from the stools collected in last 48 hours prior to the baseline visit and prior to the Week 1 visit will be calculated and the difference between those 2 visits will be calculated.

The estimand corresponding to the primary objective is:

Mean change in stool fat from baseline to Week 1 will be calculated in subjects treated with either high dose of CREON (72,000 USP units (Lipase) with meals/36,000 USP units (Lipase) with snacks) or low dose of CREON (12,000 USP units (Lipase) with meals/6,000 USP units (Lipase) with snacks) in the Evaluable Analysis Set for stool fat in the Resected Pancreatic Cancer regimen. Subjects who do not have an evaluable stool sample (described in Section 9.2.3) at both Baseline and Week 1 will be excluded from the analysis.

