12.0 Overall Type-I Error Control

The primary endpoint will be tested for each treatment group (high dose, low dose) in resected population separately at 2-sided alpha level of 0.05. Multiplicity adjustment is not planned for the primary endpoint analysis, as well not planned for any secondary endpoint analysis, as this study is not intent for registrational purpose or drug label enhancement.

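### SAP 9.3.2 replaces the protocol's within-cohort paired t-test with ANCOVA LS means, without explanation; with the usual model SE, the primary CIs and tests are too liberal for each cohort's mean change

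*SAP*

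**What the plan says.** **Endpoint.** Protocol 3.2: "The primary endpoint is change in stool fat from Baseline (Day 1) to Week 1 (Day 8) for each dose cohort in Resected Subjects".

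**Protocol analysis.** Section 7.3, Primary Analysis, gives each question its own method. For the change within a cohort: "Within each dose cohort, a paired t-test will be performed to test the null hypothesis". For the dose contrast: "For comparison between dose cohorts, the change from Baseline will be analyzed using an analysis of covariance model".

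**SAP analysis.** Section 9.3.2 fits a single ANCOVA with treatment and baseline stool fat, and then: "The least square mean estimates for change in stool fat along with its two-sided 95% CI will be provided for each treatment group". Each group is tested at two-sided 5%. Neither the test statistic nor the SE is named. Section 9.3.3 reuses the model in the subjects with complete collection, and Section 9.4.1 uses it for the dose contrast. No paired t-test for stool fat appears anywhere in the SAP.

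**Target.** SAP 2.1: "Mean change in stool fat from baseline to Week 1 will be calculated in subjects treated with either high dose of CREON" (or the low dose). SAP Table 2: "Mean Change in stool fat from Baseline to Week 1 for each dose cohort separately". Neither says that inference is conditional on the observed baselines.

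**Record of the change.** SAP 1.0 says that analyses differ from protocol version 3.0 and adds: "Details are outlined in Section 12.0". Section 12.0 deals with alpha and multiplicity ("Multiplicity adjustment is not planned for the primary endpoint analysis") and does not mention the test. Section 13.0 lists only the original version.

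**The concern.** A named primary test was replaced, and the place where the reader is sent for the explanation does not give one.

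The substitute also answers a slightly different question. The natural reading of 9.3.2 is a t-test of the LS mean with the model SE. That SE treats the mean baseline as a fixed number and uses one pooled residual variance. It is valid for the mean change at the observed baselines, given a common slope and variance. For the mean change in the population that a cohort represents, it leaves out the variation that baseline contributes. It also ignores any difference in SD or slope between cohorts. Some correlation between baseline and change is expected, because baseline is part of the change.

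At stake are the error bars on the primary endpoint: intervals labelled 95% that cover less, and overstated evidence when the true change is small.

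**Working it through.** **Inputs.** From Protocol 7.3 and SAP 2.4: 72 subjects, 16% dropout, 60 evaluable (30 per cohort), two-sided 0.05, and SD of change 25 g (or 15 g as an alternative scenario). Assumed: r, the correlation of baseline with change; normal data.

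**1. The plan's own figures.** 60/(1 - 0.16) = 71.4, rounded up to 72. With noncentral t:
- Paired, n = 30, 20 g with SD 25 g: noncentrality 20/(25/√30) = 4.38, power 98.8% (stated 99%).
- Paired, n = 30, 10 g with SD 15 g: noncentrality 3.65, power 94.2% (stated 94%).
- Two-sample, 30 per arm, SD 25 g: 86.1% at 20 g and 62.8% at 15 g (stated 86% and 63%).

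The within-cohort powers are therefore those of the paired t-test.

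**2. What the model SE leaves out.** With equal arms, the LS mean of cohort 1 is (mean change in cohort 1) - b × (difference between the two cohorts' baseline means)/2. With a common slope and equal SDs:
- true variance ≈ (SD²/n)(1 - r²/2)
- model variance ≈ (SD²/n)(1 - r²)
- ratio of model SE to true SE ≈ √[(1 - r²)/(1 - r²/2)]

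At r = -0.5 and SD 25 g these are (625/30) × 0.875 = 18.2 and (625/30) × 0.75 = 15.6 g², a ratio of 0.93. The implied size is 2[1 - Φ(1.96 × 0.926)] ≈ 7.0%.

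**3. Range for r.** With equal SDs at both visits, r = -√[(1 - ρ)/2], where ρ is the correlation between visits. Values ρ = 0.8, 0.7, 0.5, 0.3 and 0 give r = -0.32, -0.39, -0.5, -0.59 and -0.71.

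**4. Simulation.** 100,000 trials per cell, 30 per arm, bivariate normal, true change zero, equal SDs, common slope, 57 df:

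| r | SE ratio | Size of nominal 5% test | Coverage of 95% CI |
|---|---|---|---|
| 0 | 1.00 | 5.0% | 95.0% |
| -0.2 | 0.99 | 5.1% | 94.9% |
| -0.32 | 0.97 | 5.6% | 94.4% |
| -0.39 | 0.96 | 6.0% | 94.0% |
| -0.5 | 0.93 | 6.9% | 93.1% |
| -0.59 | 0.89 | 8.1% | 91.9% |
| -0.71 | 0.81 | 10.7% | 89.3% |

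The paired t-test stays at 4.9-5.1%. With 36 per arm the LS-mean test has size 6.9% at r = -0.5 and 10.6% at r = -0.7, so a larger sample does not help. Fitting a separate ANCOVA in each cohort is worse (8.7% and 15.5%).

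**5. Practical effect at SD 25 g, r = -0.5:**

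| | Model SE | LS mean, unconditional SE | Paired t |
|---|---|---|---|
| CI half-width | 7.9 g | 8.6-8.7 g | 9.3 g |
| Rejection at a true 5 g change | 25% | 20-21% | 18% |

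At the planned effects, for r from 0 to -0.71, rejection is 99.0-100% (LS mean) against 98.8% (paired t) for 20 g with SD 25 g, and 94.6-99.4% against 94.1% for 10 g with SD 15 g.

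**6. Stress tests only.** The documents assume the same SD in both cohorts. At r = -0.5, sizes in the smaller-SD and larger-SD cohort are 5.2% and 8.6% for SDs 22/25 g, 4.0% and 9.8% for 20/25 g, and 1.4% and 13.0% for 15/25 g. With unequal slopes (r = -0.3 and -0.7, both SDs 25 g), sizes are 8.5% and 5.5%.

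**The case against.** The best defence is that the LS-mean test is exact for the mean change at the observed baselines, given equal SDs and a common slope. A simulation against that target gives 4.8-5.2% at every r from 0 to -0.71. The SAP does not say that inference is to a wider population, and its estimand is set in the evaluable set itself. This is correct as far as it goes. But the SAP does not state conditioning either, and a target of mean change for each cohort separately fits the protocol's test more naturally.

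Other points on that side:
- The SAP does not name the SE, so the miscalibration rests on the natural reading. True; the omission is itself part of the defect.
- r is unknown, and at -0.2 to -0.39 the size is only 5.1-6.0%. True; hence a range is given.
- The unequal-SD figures are not the plan's assumptions. True; they carry no weight for severity.
- The study is not for registration, and planned-effect rejection barely moves. True, but SAP 12.0 uses the first point only to justify unadjusted testing. It does not justify an interval that misses its stated coverage.
- The protocol leaves details to the SAP. Replacing the named primary test is more than a detail, and the SAP's own pointer for changes does not cover it.

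**Conclusion.** The concern holds. The undocumented departure from the protocol's primary test is plain from the two texts and needs no assumption. The calibration part rests on three conditions: the usual model SE, the population mean change of each cohort as target, and a non-zero correlation between baseline and change. Under these, with 30 per arm, equal SDs and a common slope, true size runs from 5.0% at r = 0 to 10.7% at r = -0.71, and coverage from 95.0% to 89.3%. If the cohort SDs differ, the error can run in opposite directions in the two cohorts.

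The conclusion at the planned 10-20 g effects is unlikely to change. The between-dose ANCOVA comparison is not in question. This should be fixed because it concerns the primary endpoint's intervals and the remedy is cheap.

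**What to change.** In SAP 9.3.2 and 9.3.3, do one of the following and name the test statistic and SE:
- **(a)** Restore the paired t-test in each cohort with its t-based 95% CI. This is the simpler option and matches the stated power.
- **(b)** Keep the LS means with an unconditional, cohort-specific SE. For equal arms, SE² = s²(change - b × baseline/2)/n in the cohort's own arm + (b²/4) × s²(baseline)/n in the other arm + a term for the estimated slope, with n - 1 df. Its simulated size is 4.6-5.1% for SDs 25/25, 22/25, 20/25 and 15/25 g at r = -0.32, -0.5 and -0.71. Adding the baseline term to the pooled-variance SE is not enough if SDs differ: at r = -0.5 it gives 3.5% and 6.3% for 22/25 g, and 0.8% and 10.2% for 15/25 g.

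Keep the ANCOVA for the dose contrast in 9.4.1. Describe the change from the protocol, with its reason, in the section to which SAP 1.0 points.

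For consistency, use the same approach for the within-cohort tests in 9.4.2 and 9.4.4 and the non-resected test in 9.4.1. The protocol names no test for these, and no size figures are claimed for them. SAP 2.4 says that no formal tests are planned in the non-resected cohort, so that must first be reconciled with 9.4.1.

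**Cost:** SAP wording, and a wider within-cohort interval (at SD 25 g and r = -0.5, half-width from 7.9 g to 8.6-9.3 g). No stated power is lost, since 99% and 94% already describe the paired t-test.
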